1. SYNOPSIS

Title	A Multi-national, Multi-center, Prospective, Randomized, Double Blinded, Placebo-controlled Trial to Evaluate the Efficacy of HyperBox Cyclical Topical Wound Oxygen Therapy (TWO ₂) in the Treatment of Chronic Diabetic Foot Ulcers
Objectives	To evaluate the efficacy, safety and economic benefits of Cyclical Topical Wound Oxygen (TWO ₂) Therapy in the treatment of chronic diabetic foot ulcers
Device	HyperBox Cyclical Topical Wound Oxygen Therapy (TWO ₂) System applied 5 times weekly for 90 minutes for up to 12 weeks
Comparator treatment	Identical control device without cycling pressure of oxygen
Trial design	Double-blinded, multi-center, prospective, randomized, clinical trial
Setting	All subjects will be treated in a home care environment (home or equivalent facility)
Primary endpoint	Incidence of complete wound closure within 12 weeks
Secondary endpoints	
 • Time to complete wound closure • Change in wound size over time • Incidence of recurrence • Incidence of amputation • Incidence of adverse events and adverse device effects • Quality of Life – Pain, Mood and Function • Economic Analysis (EQ-5D, dressing and related medical history)
Type of subjects	
 • Foot ulcer below or at the malleoli graded as Grade 1 or 2 as assessed via the University of Texas Classification • Adequate perfusion with ABI > 0.7 AND TcpO₂ > 30mmHg OR skin perfusion > 30mmHg OR Toe pressure > 30mmHg OR Duplex with biphasic waveforms below the knee • Ulcer size \geq 1 cm² and < 20cm² after debridement • Ulcer duration \geq 4 weeks but \leq 1 year • Wound size reduction in a 2-week run-in period of \leq 30%
Number of centers	Up to 30 centers in the US, Canada and Europe
Number of subjects	Conservative sample size estimation suggested a total sample size of 220 subjects. The trial will be using a group sequential design (GSD) allowing for interim analyses to be performed after one third of subjects complete 12 weeks and two thirds of subjects complete 12 weeks and potentially stopping the trial if stopping criteria are met.
Length of Study	It is estimated that subject recruitment of 73 subjects will take about 6 months.

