3. OVERALL STUDY DESIGN AND PLAN

3.1. Overview

This is a multi-center trial, to be conducted at up to 30 sites in the United States, Canada, and Europe.

Inclusion criteria for participation in the trial include the presence of documented diabetes (Type I or II) with non-healing, full-thickness, University of Texas Classification of Diabetic Foot Ulcers Grade 1 and 2 diabetic foot ulcers of at least 4 weeks duration, but not greater than 1 year, measuring 1cm² or greater and less than or equal to 20 cm².

Subjects will be asked to sign a written informed consent form, approved by an IRB/Ethics Committee, prior to participation in the trial at the screening study visit. Each subject will be assigned a Subject Identification Number, which will be used for identification purposes in order to ensure subject confidentiality. All subject data held on the study Sponsor's database will be anonymised and identifiable only by Subject Identification Number.

Those who continue to meet all of the eligibility criteria after the 2 week run-in period will be enrolled into the trial and randomized to one of two treatment arms: TWO₂ therapy or, Control therapy.

In this trial a maximum of 220 subjects will be recruited. A Group Sequential Designs (GSD) with interims analyses after one third and two third recruited subjects has been chosen that will allow the trial to be stopped if TWO₂ therapy is obviously better than control therapy.

Subjects will be recruited as outpatients in participating wound care centers and clinics. At the screening visit the informed consent document must be signed, the wound will be measured and the subject will receive a standardized off-loading device for weight bearing wounds. The subject will from then on, be treated with predefined dressings used in the total treatment phase of the study.

A diary card will be given to every subject. Subjects will be instructed on keeping the simple diary card to record the use of the TWO₂ or control device, dressing changes and to collect data for health economic analysis. A study ID card will also function as an alert to other providers of participation in a clinical study (example Appendix I).

After a run-in period of 2 weeks the subject will be randomized into the study if the wound-size reduction is less than 30% of the initial measurement and all other inclusion and exclusion criteria are met.

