9 STATISTICAL ANALYSIS

9.1 Sample Size and Power Analysis

All sample size estimations in this section of the protocol were undertaken using the sampsi function in Stata 11 (Statcorp LP, Texas, USA). Comparisons of groups was made assuming no continuity correction.

Little data are available on similar studies using topical oxygen therapy within randomized clinical trials making sample size estimation problematic. Large trials of dermal substitutes and negative pressure have been undertaken that can be used to indicate the potential healing in the control group. The three large trials have control healing of between 18% and 28.9% around 12 weeks after entering the trial, with a mean of 28%.^{25,27,29}

The expected improvement in healing using the active device is more problematic as there have been few comparative studies published. Aburto and Frye undertook a randomized study of 20 venous ulcers and 20 diabetic foot ulcer patients.⁴² Topical oxygen demonstrated higher healing in the DFU patients after 90 days of 90% versus 40% in the control group. Blackman et al randomized 28 patients with DFUs and obtained a similar response (82.4% versus 45.5%).²² The potential difference between treatment groups was therefore 50% and 36.9% respectively. Using these studies a total sample size of 28 and 52 would be expected based on 80% power at the 5% level of significance. Neither of these studies was blinded. It is therefore likely that the effect is likely to be substantially smaller than that experienced in these two studies.

Because of the small size of these trials and lack of blinding it has been decided to offer a more cautious approach to the calculation of sample size based on a smaller expected benefit of oxygen therapy. By combining the results of the two randomized studies already undertaken the control group achieved a healing rate of 9/21 (42.8%). In the actively treated group healing occurred in 23/27 (85.2%). Assuming an expected control rate of 43% and a difference of half that experienced in these trials of 21% (to 64%) would require a sample size of 88 patients in each group (total=176), with a power of 80% and a level of significance set at $p<0.05$.

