In order to overcome the uncertainty surrounding the expected benefit, the trial will be undertaken using group sequential design (GSD) allowing for interim analysis to be performed at intervals during the trial recruitment. The interim analysis will take place after one third of subjects have been recruited, after two thirds and then a final analysis at full recruitment. The Pocock method of interim analysis will be used, which requires an equal level of significance ($p<0.022$) over the three analyses.⁴³ If the difference in primary outcome produces a probability less than this in any of the analyses then the null hypothesis is rejected and the alternative hypothesis of a difference in healing has been shown. In order to achieve this level of significance a total of 110 patients need to be recruited to each arm of the trial (total=220).

Since all patients will achieve a 12 week end point (healed versus unhealed) no uprating of this sample size will be made to take into consideration patients lost to follow up (see section 9.2).

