9.3 Primary outcome analysis

The primary endpoint is the “Incidence of complete wound closure within 12 weeks”.

The null hypothesis to be tested is that there is no difference between treatment groups in terms of the rate of wound healing after 12 weeks of study treatment. The alternative hypothesis is that such a difference exists.

Uncorrected Chi squared analyses will be used to determine the difference between treatment groups in terms of wound closure rate within 12 weeks, at the interim analysis. 95% confidence intervals will be estimated using the normal approximation interval.

Logistic regression analysis will be used to determine the effects of confounding on the primary outcome at the trial end. In particular, gender, age, ulcer duration, size and diabetic factors will be considered in the model. A stepwise procedure will be used to eliminate non-significant covariates from the model. The effect of different centers' outcomes will be entered as a random effect into the model.

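### Section 9.1's 220 subjects is a single-look size at p<0.022: the stated three-look Pocock design needs about 206 for 80% power, and 220 gives about 83–84%

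*Combined protocol and SAP*

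**What the plan says.** Section 9.1 states that "All sample size estimations in this section of the protocol were undertaken using the sampsi function in Stata 11", without continuity correction. From a control rate of 43% and a difference of 21 points (to 64%), it obtains 88 per arm, 176 in total, at 80% power and p<0.05.

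It then adopts a three-analysis Pocock design at p<0.022 per analysis, with this rule: "If the difference in primary outcome produces a probability less than this in any of the analyses then the null hypothesis is rejected". The next step reads "In order to achieve this level of significance a total of 110 patients need to be recruited to each arm of the trial (total=220". Section 9.1 makes no increase for loss to follow-up.

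The total reappears in the synopsis ("Conservative sample size estimation suggested a total sample size of 220 subjects") and in Section 3.1 ("In this trial a maximum of 220 subjects will be recruited"). Section 9.6 places the interim analyses after 73 and 146 subjects. The 80% is attached only to the 176-subject fixed design; nowhere is a power stated for 220.

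**The concern.** A sample size delivers power, not a significance level. In a group sequential design, power is the chance of crossing the boundary at any look. Raising a fixed-sample size by tightening alpha to the per-look level counts the price of the interims (a stricter final test) but not their benefit (two earlier chances to reject). The result is too large for the power it was meant to give.

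At stake is whether the maximum size is described correctly. Anyone who recomputes the design with group sequential methods will not get 220 at 80% power, and the trial report would inherit an unexplained figure.

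**Working it through.** **Inputs.** Control 43%, active 64%, 80% power, no continuity correction, Stata sampsi, boundary 0.022 at three looks, 110 per arm (Section 9.1). Two-sided test, since "The alternative hypothesis is that such a difference exists" (Section 9.3). Uncorrected chi-squared (Section 9.3). Looks at 73, 146 and 220 (Sections 9.1 and 9.6).

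**Step 1: reproduce the plan's figures.** The fixed-sample formula is

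n per arm = [z(α/2)·√(2·p̄·(1−p̄)) + z(power)·√(p₁q₁+p₂q₂)]² / (p₂−p₁)²

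with p̄ = 0.535, 2·p̄·(1−p̄) = 0.49755, p₁q₁+p₂q₂ = 0.2451 + 0.2304 = 0.4755 and (0.21)² = 0.0441.

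- α = 0.05: (1.960 × 0.7054 + 0.8416 × 0.6896)² / 0.0441 = 87.4, so 88 per arm. This matches.
- α = 0.022: (2.290 × 0.7054 + 0.8416 × 0.6896)² / 0.0441 = 109.3, so 110 per arm. This matches.
- At α = 0.022, a one-sided version gives 91 and a continuity-corrected version 119. Neither fits.

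So 110 per arm is the two-sided single-look size at 0.022. Its single-look power is 80.3%.

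**Step 2: check the boundary.** With z = 2.290 at information 1/3, 2/3 and 1, and correlations √(tⱼ/tₖ) between looks, the chance of crossing at any look under the null is 0.0499. The exact Pocock level for three equal looks is 0.02205, so 0.022 is right.

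**Step 3: size for 80% power over three looks.** The final-look drift needed is 3.0265. The fixed design at α = 0.05 needs 1.960 + 0.842 = 2.802. The inflation factor is (3.0265/2.802)² = 1.167.

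- From the rounded 176: 176 × 1.167 = 205.4, so 206.
- From the unrounded 87.4 per arm: 87.365 × 1.167 = 101.96, so 102 per arm, 204 in total.
- Pooled variance throughout: 3.0265² × 0.49755/0.0441 = 103.3, so 104 per arm, 208 in total.
- Unpooled variance throughout would be lower: 3.0265² × 0.4755/0.0441 = 98.8, so 99 per arm, 198 in total. Simulation of the planned chi-squared test does not support so small a number: 100 per arm gives 78.1%.

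**Step 4: overall power at 206 and 220.**

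| Method | 206 | 220 |
|---|---|---|
| Inflation-factor scale: drift 2.802 × √(n/88) or √(n/87.365) | 80.1–80.4% | 82.7–83.0% |
| Pooled variance | 79.9% | 82.5% |
| Unpooled variance | 81.7% | 84.2% |
| Simulated chi-squared | 79.9–80.4% | 84.3–84.6% |

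The simulated range for 220 runs from 84.3% with looks at 73/146/220 subjects to 84.4–84.6% with 37/73/110 per arm. Cumulative power at 73, 146 and 220 subjects is about 30%, 65% and 84%.

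**Step 5: size of the gap.** 220 − 206 = 14 subjects, and 14/206 = 6.8%. In power, 220 exceeds 80% by about 3 to 4 points.

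**Step 6: look sizes.** 220/3 = 73.3 and 2 × 220/3 = 146.7. The stated 73 and 146 follow from one third and two thirds of the stated maximum.

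**The case against.** The strongest reply is that the plan states no false power. It ties 80% to 176 subjects only and calls its estimate conservative, and sizing the last look at 0.022 is a cautious shortcut. Part of this stands: no power is stated for 220, so the plan cannot be said to contradict a stated one. That the single-look calculation was used is also an inference, though a firm one, from the named software and the exact match.

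The rest does not explain the excess. The cautious element in Section 9.1 is the halved treatment effect, and that is already in the 88. Loss to follow-up is expressly not allowed for. Section 9.1 presents 110 per arm as what must be recruited, not as a cushion.

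A reader might infer three stronger things that the documents do not support:

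- **That the interim looks are wrong.** They are not: 73 and 146 are the stated fractions of 220, and a constant Pocock boundary is valid for any maximum size. With 37 per arm at look 1, the simulated type I error is 5.5–5.7%. That comes from the discreteness of the chi-squared test and is separate from the sizing.
- **That the trial is underpowered.** The error runs the other way.
- **That the maximum should be cut to 206.** Section 9.2 counts deaths, amputations and losses as failures, and no loss rate is given. As an assumption, let losses be equal in both arms and let 43% and 64% exclude such failures. At 3% loss, 220 gives about 80–82% and 206 about 77%. At 5%, 220 gives about 78–80.5% and 206 about 75–76%. At 10%, 220 gives about 74–76% and 206 about 70–71%. If missing subjects are instead omitted, as Section 9.5 says, 6% loss leaves 220 × 0.94 = 206.8 subjects. Small losses therefore use up the surplus.

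Two conditions also limit the 83–84% itself. Section 8.2.11 allows an interim stop for no clear benefit, with no threshold, which would lower power. Section 9.3 names the chi-squared test for the interim analysis and logistic regression for the trial end, whereas the calculation uses chi-squared at every look.

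**Conclusion.** The point holds as a minor error in the sizing. The 110 per arm that Section 9.1 calls necessary is the single-look size at two-sided 0.022, not the size that the stated three-look rule needs. For 80% power that rule needs about 206 subjects (204 to 208 on the inflation-factor and pooled-variance scales, supported by simulation). At 220 the overall power is about 83–84%, with a range of 82.5–84.6% by method.

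All these figures assume 43% versus 64%, equal allocation, equally spaced looks, no dilution from losses counted as failures, and no futility stop. The nominal type I error, the boundary and the look sizes are unaffected.

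**What to change.** Keep the maximum of 220 and the looks at 73 and 146. In Section 9.1, replace the sentence that derives 110 per arm with a group sequential calculation (Pocock, three equally spaced looks, two-sided 5%). State that 220 gives about 83% overall power under 43% versus 64% with no losses, and that 80% would need about 206. Describe the difference as a margin, and do not reduce the maximum to 206. Add a matching line to the synopsis.

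The cost is one revised sentence in Section 9.1 and one line in the synopsis. No subjects, visits, boundaries or analyses change.

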2. INTRODUCTION

2.1. Background and Rationale

Foot disorders, such as ulceration, infection and gangrene are a major source of morbidity and a leading cause of hospitalization for persons with diabetes.¹ Ulceration, infection, gangrene, and amputation are significant complications of the diabetic foot ulcer and are estimated to cost billions of dollars each year.²

Foot disorders are also the leading causes of hospitalization in patients with diabetes mellitus.² Diabetic peripheral wounds are a major risk factor for lower extremity amputation.³ Approximately 40-70% of all lower extremity amputations are performed in patients with diabetes, and some 100,000 non-traumatic lower-limb amputations were performed among U.S. diabetics in 2008 alone.⁴ Even superficial diabetic wounds are often difficult to treat and show high rates of complications.⁵

Oxygen (O₂) is essential to wound healing. Local tissue hypoxia, caused by disrupted or compromised vasculature, is one key factor that limits wound healing.^{6,7} It is well established that O₂ is vital in the synthesis of collagen, enhancement of fibroblasts, angiogenesis and leukocyte function.⁸⁻¹⁰ O₂ also has key functions in energy metabolism^{11,12} and in the inhibition of microbial growth.¹³

Clinical use of O₂ to promote wound healing began in the 1960's with the administration of systemic full body Hyperbaric Oxygen Therapy (HBO) to treat wounds.¹³ Today HBO is usually administered in single or multi place chambers utilizing pressures of 2,500 mb and higher. HBO is reimbursed by the Center for Medicare and Medicaid Services in the US to treat certain wounds, including Diabetic Foot Ulcers (DFU's). A Cochrane review by Kranke et al. demonstrated that in people with foot ulcers due to diabetes, HBO significantly reduced the risk of major amputation and may improve the chance of healing at one year.¹⁴ The availability of HBO facilities, contraindications, the need to transfer the patients to the HBO facilities and the risks of undesired systemic side effects, limits the widespread use of HBO to treat diabetic ulcers on a global basis.

In an effort to address some of these drawbacks, the principle of topical pressurized oxygen administration or topical wound oxygen therapy (TWO₂) was introduced in the late 60's.¹⁵ The approach of topically oxygenating the wound is quite different from HBO. TWO₂ does not involve pressures anywhere near as high as in HBO. Additionally, TWO₂ is portable and can be administered in varied care sites, including in the patient's home. There have been a number of studies, including smaller Randomized Control Trials (RCTs) and Case Series etc., published demonstrating very positive outcomes with TWO₂.¹⁵⁻²²

A previous study with the cycling TWO₂ device in a prospective, controlled clinical trial conducted in Canada examined the clinical efficacy of the TWO₂ device used in this proposed RCT. In outpatients with severe diabetic foot ulcers referred for care to a community wound care clinic, 14 out of 17 ulcers (82.4%) in the treatment group and 5 of 11 ulcers (45.5%) in the control group healed within 90 days. The median of wound healing in the oxygen group was 56 vs. 93 days in the control group (p = 0.04).

The concept of topical oxygen is still relatively unknown to the medical community as a whole and a larger well conducted randomized clinical trial is clearly needed to establish topical therapy as an important treatment in the management of diabetic foot ulcers.

This trial will evaluate the efficacy and potential economic benefits of TWO₂ in the treatment of chronic diabetic foot ulcers. Pre-trial and real-time events captured for each subject will be

used to provide data for health economic analyses.

2.2. Medical Device

The medical device being investigated in this trial is the HyperBox Cyclical Topical Wound Oxygen therapy (TWO₂) system manufactured by AOTI Ltd., Galway, Ireland.

The TWO₂ System operates by applying cyclical oxygen pressure directly to the wound site within a sealed and humidified environment. This provides a greater tissue oxygen diffusion gradient and increased tissue oxygenation, which enhances antimicrobial actions, stimulates angiogenesis and maximizes collagen production. The cyclical nature of the pressure also creates a sequential compression effect which helps reduce peripheral edema and stimulates wound site perfusion.

The TWO₂ system is intended as adjunctive therapy to standard wound care for acute or chronic wounds. It can be placed over a wound on the lower leg and when connected to a medical grade oxygen supply (Wall supply, Oxygen Concentrator or LOX system) which provides oxygen directly to the wound site with a pressure cycling between 5 to 50mbar at a frequency of approximately 2 cycles per minute. An integrated humidifier aids in keeping the wound moist during treatments.

The devices have US Food and Drug Administration (FDA) 510(k) clearance, Health Canada clearance and CE-Mark approval for the following indications:

Treatment of acute and chronic wounds on the lower extremity, such as;
Diabetic ulcers, Venous stasis ulcers, Post-surgical wounds, Gangrenous lesions,
Decubitus/pressure ulcers, Amputations/infected stumps, Skin grafts, Burns, Frostbite.

2.3. Risk-Benefit Assessment

The HyperBox Cyclical Topical Wound Oxygen Therapy System is a non-invasive device that has been assessed to provide Non Significant Risk (NSR) per FDA guidelines. The device offers the same therapy as the predicate system, which has been used in the marketplace for over 20 years with no recorded adverse events. Based on this assessment the potential benefit of the therapy is expected to exceed any potential risks envisioned.

2.4. Compliance Statement

This trial will be conducted in compliance with the approved study protocol and ISO 14155:2011 (E) Clinical investigation of medical devices for human subjects — Good clinical practice as reflected in Good Clinical Practice in accordance with the International Conference on Harmonisation (ICH) E6: "Good Clinical Practice: Consolidated Guideline," 62 Federal Register 25,692 (1997) where and as adopted by the FDA, and applicable regulatory requirements. Investigators should conduct the trial in compliance with these conditions, agreed to with AOTI, Ltd. and approved by Regulatory Authorities and IRB/Ethics Committees. Signature of the protocol by the investigator(s) and AOTI, Ltd. confirms this agreement.

3. OVERALL STUDY DESIGN AND PLAN

3.1. Overview

This is a multi-center trial, to be conducted at up to 30 sites in the United States, Canada, and Europe.

Inclusion criteria for participation in the trial include the presence of documented diabetes (Type I or II) with non-healing, full-thickness, University of Texas Classification of Diabetic Foot Ulcers Grade 1 and 2 diabetic foot ulcers of at least 4 weeks duration, but not greater than 1 year, measuring 1cm² or greater and less than or equal to 20 cm².

Subjects will be asked to sign a written informed consent form, approved by an IRB/Ethics Committee, prior to participation in the trial at the screening study visit. Each subject will be assigned a Subject Identification Number, which will be used for identification purposes in order to ensure subject confidentiality. All subject data held on the study Sponsor's database will be anonymised and identifiable only by Subject Identification Number.

Those who continue to meet all of the eligibility criteria after the 2 week run-in period will be enrolled into the trial and randomized to one of two treatment arms: TWO₂ therapy or, Control therapy.

In this trial a maximum of 220 subjects will be recruited. A Group Sequential Designs (GSD) with interims analyses after one third and two third recruited subjects has been chosen that will allow the trial to be stopped if TWO₂ therapy is obviously better than control therapy.

Subjects will be recruited as outpatients in participating wound care centers and clinics. At the screening visit the informed consent document must be signed, the wound will be measured and the subject will receive a standardized off-loading device for weight bearing wounds. The subject will from then on, be treated with predefined dressings used in the total treatment phase of the study.

A diary card will be given to every subject. Subjects will be instructed on keeping the simple diary card to record the use of the TWO₂ or control device, dressing changes and to collect data for health economic analysis. A study ID card will also function as an alert to other providers of participation in a clinical study (example Appendix I).

After a run-in period of 2 weeks the subject will be randomized into the study if the wound-size reduction is less than 30% of the initial measurement and all other inclusion and exclusion criteria are met.

All subjects will receive 90 minutes of either TWO₂ therapy or control therapy at their home or nursing care facility 5 times a week for the treatment phase of up to 12 weeks. To secure double blinding no TWO₂ treatment will be done at the study centers. Delivery, installation and training on use of the TWO₂ device or control device may differ according to geographical location and shall be performed by trained accredited home health service providers utilizing nurses or other registered healthcare providers, or by trained home/durable medical equipment (DME) providers and an expert on the TWO₂ device or control device. The subject, or in some cases caregiver or healthcare professional (such as a home health nurse or aide), applying the TWO₂ therapy or control therapy will be adequately trained and assessed for competency on the use of the device, which will be reviewed monthly. Dressing changes at home (or equivalent) may be performed either by the subject, caregiver or healthcare professional such as a home health nurse or aide. Both the TWO₂ therapy and control therapy groups will visit the study center once per week for on

treatment study visits. Dressings will be pre-specified advanced moist wound therapy (AMWT) dressings, which will be changed at a minimum of once weekly according to the PI/Subl Investigator's (Subl) clinical judgment. Subjects will receive standardized off-loading for a weight bearing wounds or an open heel boot for posterior heel wounds. A Charcot Restraint Orthotic Walker boot (CROW boot) may be used where there is a need to protect a Charcot Foot deformity. Debridement will be performed as needed according to the PI/Subl clinical judgment.

The treatment phase of the study will be 12 weeks. At every on treatment study visit at the clinic, foot ulcers are photographed. The initial (baseline) measurement after debridement will serve as the standard. Digital images will be sent to a blinded central assessor to be assessed and measured.

Once wounds are initially considered closed, that visit will serve as the first of two confirmatory visit. All subjects will continue treatment for an additional 2 weeks, to confirm wound closure.²³ During this period, subjects will continue to receive TWO2 therapy or Control therapy, use and change dressings, and use the off-loading device, where it is required, per the protocol. For subjects whose wounds close at week 11 or later the treatment phase will continue to the second confirmatory visit.

[figure not shown]
All subjects whose wounds are confirmed closed or who finished the treatment phase of 12 weeks – whichever is sooner - will enter into the post-treatment follow-up phase of 12 and 38 weeks.

Subjects who are withdrawn by the PI/Subl from the study treatment phase will be asked to return for the final week 12 on treatment visit and follow-up phase at 12 and 38 weeks.

The maximum duration for participation in the trial is 54 weeks. During the follow-up phase, subjects will receive standard care according to the clinician's recommendation and will be asked not to participate in another wound care trial in this period.

The start of the trial is scheduled for July 2014.

